11.4.1 Sample Size & Statistical Power

Similar to phase II TB trials, rate of CSF yeast clearance has been used in moderate size phase II cryptococcal trials to demonstrate microbiologic efficacy as proof of concept. When the EFA is better than 0.20 CFU/mL/day, there is reasonably good survival after cryptococcal meningitis (Figure 2.5). Once the EFA is better than approximately 0.30 \log_{10} CFU/mL/day, there is less obvious incremental gains in survival beyond this threshold.⁶¹

Overall, the EFA is a quantitative measure of microbiologic activity in humans of an antifungal regimen.

For the EFA on a lower-dose 5-FC, we will have 36 participants with adequate data to calculate the EFA (i.e. non-sterile CSF culture at baseline and at least 1 follow up LP) and a standard deviation of approximately 0.20.

The CSF EFA will be interpreted in the context of other antifungal regimens published EFAs and the concurrent controls (Table 2.5). For example, if the lower-dose 5-FC arm has an EFA >0.30 \log_{10} CFU/mL/day and standard deviation of ± 0.20 , then the low dose 5-FC regimen will establish superiority compared to fluconazole 1200 mg regimen and non-inferiority with the all oral 5FC + fluconazole regimen. For a low-dose 5-FC arm EFA of 0.35, non-inferiority compared to the concurrent controls will be established with a margin of 0.17. For an EFA better than $0.30 \log_{10}$ CFU/mL/day, survival is relatively similar across antifungal regimens, as per section 2.5 and Figure 2.5.

A subsequent statistical analysis of the ASTRO clinical trial has demonstrated that 30 to 40 patients with EFA is sufficient to determine a significant difference in EFA. This was based on a bootstrap analysis of the participants of the ASTRO trial that is documented in table 11.4.1 below.

Table 11.4.1: EFA Calculated with the ASTRO Study (n=378)

Replicate Size	500 Bootstrap EFAs from randomly selected replicates
N	Mean (95%CI)
10	-0.454 (-0.768, -0.219)
15	-0.450 (-0.688, -0.257)
20	-0.449 (-0.664, -0.269)
30	-0.445 (-0.608, -0.292)
40	-0.445 (-0.593, -0.308)
50	-0.446 (-0.569, -0.316)
378 Actual	-0.444 (-0.489, -0.399)

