Recently, Jezewski *et al.* endeavored to better understand the mechanisms of how flucytosine functions in the *in vivo* environment.⁶⁶ For years, 5-FC has been understood to have a synergistic effect when used in combination with amphotericin or fluconazole.⁶⁷⁻⁶⁹ However, this synergism has been poorly understood and difficult to replicate *in vitro*. One of the conditions that has been thought to potentiate the flucytosine effects is the elevated level of CO₂ in the body compared to ambient atmospheric levels. In the Jezewski *et al.* study, isolates grown at elevated CO₂ concentrations had a 2 to 64-fold reduction in MIC, depending on the CO₂ concentration. We have also found, in our own studies that the ratio of 5FC CSF concentrations to MIC is quite high, with a median ratio of 2.98 (Figure 2.4.2). These data indicate that in addition to the strong evidence by Stott *et al* above that lower doses of flucytosine will still achieve levels above MIC, the target MIC might be even lower than we have identified in our isolates (Table 2.4).

During phase 2 of the AMBITION-cm trial, which established the effectiveness of single high dose liposomal Amphotericin 10 mg/kg for induction treatment of CM. Amphotericin was paired with high-dose fluconazole without 5-FC.³⁸ In this phase 2 trial, single dose liposomal Amphotericin B 10 mg/kg with fluconazole 1200 mg/day for 14 days demonstrated an EFA of -0.52 log₁₀ CFU/mL/day. This was found to be non-inferior to the standard regimen of liposomal Amphotericin 3 mg/kg/day for 14 days with the same dose of fluconazole. These data suggest that the dose of 5-FC can be safely adjusted for optimization while maintaining the mortality benefit of CM induction therapy.

Table 2: MIC for flucytosine in *Cryptococcus* isolates from participants in the EnACT clinical trial. The top section are the MIC values for the initial screening CSF, prior to significant exposure to 5-FC. The second section is the last CSF with positive *Cryptococcus* growth during treatment. The χ^2 p-value tests for a statistical difference in MIC between the control and oral amphotericin groups.

MIC ($\mu\text{g/mL}$)	Control (n, %)	Oral Amphotericin (n, %)	Total (n, %)	χ^2 p-value
Screening Lumbar Puncture				
≤ 2	2 (14.3%)	7 (21.9%)	9 (19.6%)	0.451
4	9 (64.3%)	15 (46.9%)	24 (52.2%)	
8	3 (21.4%)	6 (18.8%)	9 (19.6%)	
16	0 (0%)	4 (12.5%)	4 (8.7%)	
Last Positive Lumbar Puncture				

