[figure not shown]
Induction Regimen	EFA	± SD	N	Ref
Single-dose Amphotericin + 5FC + fluconazole (1200 mg/day)	0.40	0.13	407	⁴³
Amphotericin	0.31	0.15	99	
Amphotericin + 5FC	0.42	0.10	100	³⁰
Amphotericin + fluconazole (800 mg/day)	0.32	0.10	99	
Amphotericin + 5FC	0.41	0.22	21	
Amphotericin + fluconazole (800 mg/day)	0.38	0.18	22	⁴⁴
Amphotericin + fluconazole (1200 mg/day)	0.41	0.35	23	
Amphotericin + voriconazole	0.44	0.20	13	
Amphotericin (5 days) + fluconazole (1200 mg/day)	0.30	0.11	30	⁴²
Amphotericin + 5FC	0.49	NA	30	⁴⁵
Amphotericin + 5FC + INF- β	0.64	NA	60	
Amphotericin (7 days) + fluconazole (1200 mg/day)	0.38	0.20	19	⁴⁶
Amphotericin (7 days) + fluconazole (1200 mg/day) + 5FC	0.50	0.15	18	
Fluconazole (1200 mg/day)	0.18	0.11	30	¹⁹
Fluconazole (800 mg/day)	0.07	0.17	30	
Amphotericin (1 mg/kg/day)	0.48	0.28	49	²⁶
Fluconazole (400 mg/day)	0.02	0.05	5	
Amphotericin + fluconazole (800 mg/day)	0.36	0.25	223	²⁵
Amphotericin + fluconazole (800 mg/day) + sertraline	0.43	0.39	128	²¹
Fluconazole (1200mg/day)	0.11	0.09	20	⁴⁷
Fluconazole (1200mg/day) + flucytosine	0.28	0.17	21	
Amphotericin 1 week (either 5FC or fluconazole)	0.40	0.24	179	
Amphotericin 2 week (either 5FC or fluconazole)	0.42	0.25	182	
Fluconazole (1200mg/day) + flucytosine	0.26	0.18	182	²
Amphotericin + 5FC	0.46	0.25	186	
Amphotericin + fluconazole (1200mg/day)	0.36	0.23	175	

Similarly, a separately published analysis found a correlation between EFA and 10-week mortality ($P=0.04$) using a larger collection of studies (Figure 2.5.B).⁴⁸ This analysis used the reported EFA from the publication, which differed slightly across publications and did not have primary data, thus was unable to account for differing demographics across highly diverse HIV-positive and HIV-negative cohorts. The included studies came from: the US, Canada, India, Thailand, Indonesia, Laos, Vietnam, Uganda, South Africa, Malawi, Botswana, Zimbabwe and Netherlands. This analysis only included randomized trials, and excluded two fluconazole monotherapy studies,^{19,26} which had poor EFAs $<0.20 \log_{10}$ CFU/ml/day and high mortality on the basis that these are clearly inferior therapies. This exclusion misses the point that EFA is a quantitative marker of microbiologic activity in humans.

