3. OBJECTIVES

3.1 Study Objectives

3.1.1 Phase II Trial Objective

To demonstrate the reduced dose of 5-FC, when combined with IV AMB for induction therapy of CM is non-inferior compared to traditional dosing of 5-FC in reducing fungal burden of *Cryptococcus*

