11. STATISTICAL CONSIDERATIONS

11.1 Statistical Analysis Plan

Descriptive statistical methods will be used to summarize the data from this study, with hypothesis testing performed for the primary efficacy endpoint. Unless stated otherwise, the term "descriptive statistics" refers to number of subjects (N), mean, median, standard deviation,

standard error, minimum, and maximum for continuous data and frequencies and percentages for categorical data. All data collected during the study will be included in data listings. Unless otherwise noted, the data will be sorted first by treatment assignment, subject number, and then by date. Unless specified otherwise, all statistical testing will be two-sided and will be performed using a significance (alpha) level of 0.05. The statistical analyses will be conducted with the SAS® software package version 9.4 or higher or R Studio® 2022.07.1 or higher. All analyses will be subject to formal verification procedures. Analysis will be by intent-to-treat principle.

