11.3 Statistical Hypothesis

We hypothesize that a regimen with lower-dose 5-FC will be well tolerated, have reduced toxicity compared to a regimen with standard dose 5-FC, will have a superior rate of CSF fungal clearance compared to historical fluconazole monotherapy, and will have a statistically non-inferior rate of CSF fungal clearance compared to the historical standard-dose 5-FC. Full details of statistical considerations for making comparisons with historical controls will be provided in Statistical Analysis Plan.

11.4 Primary Endpoint:

The primary endpoint is CSF early fungicidal activity (EFA) during induction treatment: as measured in the change in \log_{10} CFU/mL of CSF/day and as assessed with general linear models. EFA from the low-dose 5-FC group will be compared to historical controls of standard-dose IV amphotericin + standard dose flucytosine and fluconazole.

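### The only non-inferiority margin given against standard-dose 5-FC (0.17 log10 CFU/mL/day) is larger than every within-trial estimate of the 5-FC effect on amphotericin in Table 2.5 (0.00 to 0.12)

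*Combined protocol and SAP*

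**What the plan says.** Section 3.1.1 sets out to demonstrate that the reduced dose "is non-inferior compared to traditional dosing of 5-FC in reducing fungal burden". Section 11.3 hypothesises that the regimen "will have a statistically non-inferior rate of CSF fungal clearance compared to the historical standard-dose 5-FC", and section 11.1 describes the analysis as descriptive "with hypothesis testing performed for the primary efficacy endpoint".

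The only number attached to that test is in section 11.4.1, as an example: "For a low-dose 5-FC arm EFA of 0.35, non-inferiority compared to the concurrent controls will be established with a margin of 0.17". The control EFA, number of controls, power, and share of the 5-FC effect to be kept are not stated with it. Section 11.3 says that "Full details of statistical considerations for making comparisons with historical controls will be provided in Statistical Analysis Plan". Section 11.1, which carries that title, gives no margin, and no other margin against standard-dose controls appears in the supplied text.

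Section 4.1 describes a single-arm trial with historical AMBITION controls, so there are no concurrent controls.

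**The concern.** The trial asks whether a lower dose of 5-FC still does what standard-dose 5-FC does. The new regimen keeps amphotericin and fluconazole, so the most it can lose through under-dosing is the contribution of 5-FC itself. If the margin exceeds that contribution, a dose that had lost all of it could still be declared non-inferior. The result could then be read as support for reduced dosing that the data do not give, on an endpoint that the protocol links to mortality.

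**Working it through.** **1. Can 0.17 be reproduced?** Inputs from 11.4.1: n = 36, SD 0.20, low-dose EFA 0.35. Control EFA, control n and power are not given, so there is no unique check. Taking margin = (control − 0.35) + (z_alpha + z_power) × SE, several unrelated assumption sets come close:
- control 0.40, 164 controls, SD 0.20, one-sided 0.025, 90% power: 0.169
- control 0.40, 36 v 36, one-sided 0.05, 80% power: 0.167
- zero true difference, 36 v 36, one-sided 0.025, 95% power: 0.170

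The figure is attainable, but its basis cannot be identified.

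**2. 5-FC effect on amphotericin, within trials (Table 2.5).** Difference of means, with SE = sqrt(SD1²/n1 + SD2²/n2):

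| Trial (reference) | With 5-FC | Comparator | Difference (95% CI) | Type |
|---|---|---|---|---|
| 2 | 0.46, SD 0.25, n 186 | + fluconazole 1200: 0.36, 0.23, 175 | 0.10 (0.05, 0.15) | replaces fluconazole |
| 30 | 0.42, 0.10, 100 | + fluconazole 800: 0.32, 0.10, 99 | 0.10 (0.07, 0.13) | replaces fluconazole |
| 30 | 0.42, 0.10, 100 | amphotericin alone: 0.31, 0.15, 99 | 0.11 (0.075, 0.145) | add-on |
| 44 | 0.41, 0.22, 21 | + fluconazole 1200: 0.41, 0.35, 23 | 0.00 (−0.17, 0.17) | replaces fluconazole |
| 44 | 0.41, 0.22, 21 | + fluconazole 800: 0.38, 0.18, 22 | 0.03 (−0.09, 0.15) | replaces fluconazole |
| 46 | 0.50, 0.15, 18 | + fluconazole 1200: 0.38, 0.20, 19 | 0.12 (0.01, 0.23) | add-on |

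The largest estimate is 0.12, and 0.17/0.12 = 1.42. The voriconazole comparator in reference 44 (0.41 v 0.44, −0.03) would only lower the range.

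Inverse-variance pool, one contrast per trial (references 2, 30, 46, 44; weights 22.5, 71.4, 4.3, 1.9%; fluconazole comparators, 1200 mg in reference 44): 0.099 (0.075, 0.122). About 96% of that weight is 5-FC replacing fluconazole. Pooling only the two add-on contrasts gives 0.111 (0.077, 0.145).

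**3. Chance of meeting 0.17 after a real loss.** SE = sqrt(0.20²/36 + SDc²/nc). The number of evaluable controls is not fixed. I assume 164 (AMBITION intervention arm in Uganda, section 4.1) down to 140 (164 less about 15% culture-negative, section 5.1), with SDc from 0.13 (single-dose row of Table 2.5) to 0.20. SE is then 0.0348 to 0.0374, and the 95% CI half-width is 1.96 × SE = 0.068 to 0.073.

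- True loss 0.10: Phi(0.07/SE − 1.96) = 0.47 to 0.52
- True loss 0.12: Phi(0.05/SE − 1.96) = 0.27 to 0.30
- Largest observed loss that meets 0.17: 0.17 − 1.96 × SE = 0.097 to 0.102

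With only 36 controls at SD 0.20 (SE 0.0471), the first two fall to 0.32 and 0.18.

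**4. The protocol's example.** Against an assumed control of 0.40 (single-dose row), the difference is −0.05 with lower limit −0.118 to −0.123. That meets 0.17 but includes a loss of 0.10. Against 0.46 (reference 2 row), the difference is −0.11 with lower limit about −0.18, which fails 0.17.

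**5. The survival levels.** 0.40 − 0.17 = 0.23. That is above the 0.20 level of section 2.5 and below the 0.30 level of the synopsis and 11.4.1.

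**6. A margin of 0.10, for comparison.** Power if the true difference is zero: Phi(0.10/SE − 1.96) = 0.76 to 0.82. If the true loss is 0.05: Phi(0.05/SE − 1.96) = 0.27 to 0.30.

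**The case against.** **It is only an example, and a SAP may set the margin.** True as to form: 11.4.1 introduces 0.17 by way of illustration and never names it as the pre-specified criterion. But it is the only figure supplied for the primary objective. If it is not the margin, the objective has none.

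**The protocol reads EFA against survival levels, not against a retained 5-FC effect.** This partly stands. A residual EFA of 0.23 clears the 0.20 level, though not the 0.30 level. But those levels concern survival at a given clearance rate. They do not show non-inferiority to standard-dose 5-FC, which is what 3.1.1 and 11.3 claim.

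**Table 2.5 contains a 5-FC effect of exactly 0.17.** It does: fluconazole 1200 mg with and without flucytosine, 0.28 v 0.11 (reference 47). Neither arm had amphotericin, which everyone here receives, and the protocol does not cite this contrast as its source.

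**The pool is mostly the wrong contrast.** This stands as a limit. Everyone in this trial takes fluconazole as well, so trials where 5-FC replaced fluconazole are indirect evidence. A reader might infer that 0.17 is proven to exceed the true 5-FC effect in this regimen. The documents do not show that: the one matching contrast, "Amphotericin (7 days) + fluconazole (1200 mg/day) + 5FC" against the same regimen without 5-FC, has an interval up to 0.23. It does not exclude 0.17, but its estimate of 0.12 and lower limit of 0.01 do not support 0.17 either.

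**The preferred backbone.** For it, section 2.4 reports that "single dose liposomal Amphotericin B 10 mg/kg with fluconazole 1200 mg/day for 14 days demonstrated an EFA of -0.52" without 5-FC, while Table 2.5 has 0.40 with 5-FC. A reader might infer that 5-FC adds nothing there. That comparison is across trials and gives no effect size; the documents hold no within-trial contrast on single-dose liposomal amphotericin.

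**Conclusion.** The concern holds. On the protocol's own evidence, 0.17 exceeds every within-trial point estimate of the 5-FC effect on amphotericin, and also the upper limits of both pools (0.122 and 0.145). Meeting it would not by itself show that any of that effect is kept. A regimen that truly lost 0.10, about the whole pooled effect, would pass in roughly 47 to 52% of trials; one that lost 0.12, in 27 to 30%.

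These rates assume 140 to 164 evaluable controls, control SD 0.13 to 0.20, and an unadjusted comparison; the adjusted mixed model of section 4.1 could change the SE.

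Two stronger readings are not supported. One is that the 0.35 example would be called non-inferior whatever the controls show: it meets 0.17 against 0.40 and fails against 0.46. The other is that 0.10 is thereby the correct margin: it lies above the pool's lower limit of 0.075 and would rule out only loss of about the whole effect.

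**What to change.** Keep n = 36. In 11.4.1:
- Remove 0.17 as the margin against the AMBITION controls, and call those controls historical instead of concurrent.
- State that the adjusted EFA difference is reported with its two-sided 95% CI (expected half-width about 0.07 with 140 to 164 controls). Read it against the Table 2.5 effect of 5-FC on amphotericin (0.10 to 0.12), noting that this comes mostly from trials where 5-FC replaced fluconazole.
- Claim non-inferiority to standard dose only if the CI excludes a margin that the sponsor justifies as smaller than that effect, with power restated. A margin of 0.10, for example, has about 76 to 82% power if there is no true difference and 27 to 30% if the true loss is 0.05; state what it does not rule out.
- Give a margin for, or reword, the sentence claiming non-inferiority to the all-oral 5-FC plus fluconazole regimen.

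If the sponsor justifies no such margin, present the comparison as estimation and align 3.1.1, 11.1 and 11.3. Either way, make any separate SAP match.

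Cost: a protocol amendment to the wording, with no added patients or visits. The downside is a less favourable stated chance of a formal non-inferiority claim, or no such claim under estimation.

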Phase II Study Drug and Dosing	
 • Participants will receive 5-FC 60mg/kg/day for 10 days. • Participants will receive IV AMB 0.7-1.0 mg/kg/day for 7 days. • Liposomal Amphotericin B single IV dose 10 mg/kg is preferred, when available. • All participants will receive fluconazole 1200 mg/day during consolidation therapy from day 1 to 14 then 800 mg/day from day 15 to 10 weeks, and 200mg/day after 10 weeks.
Phase II Monitoring	
 • All participants will have CSF quantitative fungal cultures performed on Days 1, 2-4, 5-7, and 10-14 of antifungal treatment. • 3x weekly CBC, chemistries, and kidney function tests for duration of induction therapy during hospitalization
Phase II Safety Analysis	
The Data Monitoring Committee (DMC) will conduct interim safety analysis after 10 participants are enrolled with >2 weeks of accrued data and calculable EFA.
 
EFA and culture positive Cryptococcus relapse will be monitored by the trial investigators, and if statistical evidence shows that EFA <0.2 log₁₀ CFU/mL/day, then an early DMC will be called.

Phase II Statistical Design Rationale	
Early fungicidal activity (EFA) is a quantitative measure of antimicrobial activity for an antifungal regimen in human patients with cryptococcal meningitis. In numerous trials, EFA correlates well with 10-week mortality. Specifically, EFAs worse than 0.20 log₁₀ CFU/mL/day are associated with higher mortality (>50%) and EFA better than 0.3 log₁₀ CFU/mL/day is associated with lower mortality (30-40%).
 
EFA is calculated by measuring the slope of the clearance rate of yeast from CSF, which is calculated from longitudinal quantitative CSF cultures collected over two weeks.
 
By intent to treat analysis, all participants who are enrolled in this study will be included for analysis.

Clinical Trial Sites	
 1. Mulago Hospital, Kampala, Uganda 2. Kiruddu Hospital, Kampala, Uganda 3. Mbarara Regional Referral Hospital, Mbarara, Uganda

Estimated Time to Complete Enrollment:	Up to 12 months
---	-----------------

Table of Contents

1. KEY ROLES	1
2. BACKGROUND AND SCIENTIFIC RATIONALE	2
2.1 Background Summary and Study Hypotheses	2
2.2 Burden of Cryptococcal Meningitis	2
2.3 Treatment of Cryptococcal Meningitis	4
2.4 Rationale for Optimizing 5FC Dose	6
2.5 Early Fungicidal Activity	7
2.6 Potential Risks and Benefits	10
3. OBJECTIVES	12
3.1 Study Objectives	12

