2. BACKGROUND AND SCIENTIFIC RATIONALE

2.1 Background Summary and Study Hypotheses

Cryptococcal meningitis (CM) has emerged as one of the most frequent and deadly opportunistic infections in HIV patients, with a global burden estimated at nearly 1 million cases annually.¹ Early mortality from HIV-associated cryptococcal meningitis remains unacceptably high, in large part due to the high cost, toxicity, and relatively limited repertoire of effective antifungals. The essential role of 5-FC in reducing fungal burden in the first week of therapy has now been firmly established.²⁻⁴ Importantly, access to the important medication 5-FC remains limited in settings where CM incidence and mortality is highest.

The Advancing Cryptococcal Meningitis treatment for Africa trial (ACTA) recently demonstrated in a high quality, randomized controlled trial that Amphotericin B (AMB) in combination with 5-FC had a 38% reduced mortality at 10-week follow-up when compared to fluconazole used in combination with AMB.² A cost-effectiveness analysis based on these data showed that the cost of saving 1 life from CM would be only \$973.⁵

While there are 3 stringent regulatory authority (SRA) approved manufacturers of 5-FC, for decades these companies have not been registered in Africa.^{6,7} Consequently, this low-cost, off-patent, life-saving medication has been widely unavailable in the region of the world where it is needed most. Vitaris, one of the SRA approved manufacturers of 5-FC received WHO pre-qualification to produce 5-FC tablets in 2018.⁸ This led to registration in South Africa and development of an access program that provided 5-FC free of charge to tertiary centers throughout the country.⁹ In this project, after 5-FC was provided free of charge, these centers saw an 11% mortality reduction compared to a period before 5-FC was freely available.⁹

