2.3 Treatment of Cryptococcal Meningitis

Standard cryptococcal meningitis treatment is divided into three phases: a 2 week induction phase, followed by an 8-week consolidation phase, and an extended maintenance phase thereafter for secondary prophylaxis.²⁴ Table 2.3 outlines the treatment recommendations for cryptococcal meningitis in HIV-infected individuals. Historically, international treatment guidelines have been informed primarily by large multisite clinical trials with endpoints of treatment success and survival at 2 weeks and 10 weeks. Ongoing mortality occurs between 10-18 weeks. After 18 weeks, approximately 90-95% will be alive at 5 years.^{23,25}

Table 2.3: 2018, 2022 WHO Antifungal Treatment Recommendations for Cryptococcal Meningitis

Medication and Dose	Week 1	Week 2	Week 3-10	Week >10
Amphotericin B (1.0 mg/kg/day) + flucytosine 100mg/kg/day	Yellow			
Fluconazole 1200mg daily		Yellow		
Fluconazole 800mg daily			Light Blue	
Fluconazole 200mg daily				Through 12 months

Treatment Phase	Induction	Induction	Consolidation	Secondary Prophylaxis
-----------------	-----------	-----------	---------------	-----------------------

These recommendations are based on a published 2018 phase III randomized trial.²⁰ This remains the 2022 recommended regimen for locations without access to liposomal amphotericin B (Ambisome®).²¹

[figure not shown]
In the published ACTA trial, one week of IV amphotericin B deoxycholate was non-inferior to two weeks of IV AMB (Figure 2.3).² The best therapy in the ACTA trial was 1 week of IV AMB + flucytosine with 24% (27/113) 10-week mortality.

Cryptococcal mortality can be reduced by the use of high-dose amphotericin B (0.7-1.0 mg/kg/day), alongside aggressive inpatient management of raised intracranial pressure.¹² In

most resource-limited settings, standard induction therapy for cryptococcosis includes the alternate regimen of IV AMB for 14 days combined with high-dose fluconazole (800-1200mg/day).

The ability of amphotericin to rapidly and consistently sterilize the cerebrospinal fluid (CSF) of cryptococcal patients suggests that amphotericin should be central to any induction strategy.²⁶

Figure 2.3: ACTA trial, comparison of induction therapies

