2.5 Early Fungicidal Activity

[figure not shown]
Rate of fungal clearance, or early fungicidal activity (EFA), provides a measure for evaluating the efficacy of induction therapy for CM. Bicanic *et al* have demonstrated in a pooled series of Phase II clinical trials that the rate of cerebrospinal fluid sterilization correlates with clinical outcomes.⁴⁰

Quantitative CSF culture yeast clearance is generally logarithmic over the first 2 weeks; thus, the clearance can be estimated by linear regression of log₁₀ colony-forming units (CFU) per mL

of CSF per day of therapy as a unit of measure (i.e., change in \log_{10} CFU/mL CSF/day). This approach has allowed for small innovative phase II clinical trials to estimate the early fungicidal activity of newer induction regimens with dramatically smaller sample sizes, using early fungicidal activity as a surrogate marker.

Similarly in Uganda, the relationship of EFA to 10-week and 26-week survival in patients with CM has been investigated in several clinical trials. In a series of three NIH-sponsored clinical trials from 2010 to 2018,⁴¹ an EFA worse than $0.20 \log_{10}$ CFU/ml/day was strongly associated with increased mortality ($P=0.001$). Survival was comparable among AMB regimens with EFAs greater than $0.20 \log_{10}$ CFU/ml/day.

Figure 2.5: Early Fungicidal Activity versus 26-week Survival with IV AMB + Fluconazole

Below are examples of EFA spaghetti plots (Figure 2.5.A), where each line is an individual research participant, and each dot is a CSF quantitative culture value in \log_{10} CFU/mL CSF units. In general, CSF yeast clearance is approximately linear (on a \log_{10} scale). With IV AMB, the rate of clearance improves. With IV AMB + 5-FC, the rate of clearance improves further over IV AMB + fluconazole alone. Increases in the first 1 day of therapy are common, but after Day 2 the majority have a steadily decreasing CFU/mL count over 14 days of induction therapy. The occasional outlier patient (~5%) might have increased CSF culture values over time (even with IV AMB + 5FC).

Figure 2.5.A: Example of Serial Quantitative CSF Cultures to calculate EFA

Fluconazole 400mg/day in Cape Town ²⁶	Fluconazole 1200mg/day in Mbarara, Uganda ¹⁹	IV AMB x 5day with fluconazole 1200mg in Mbarara, Uganda ⁴²	IV AMB + 5FC x 14 days in Cape Town ¹⁷
--	---	--	---

[figure not shown]

Table 2.5: Trials comparing CSF *Cryptococcus* clearance Early Fungicidal Activity (EFA) by regimen.

[figure not shown]

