The control cohort will be drawn from the AMBITION trial that was conducted partly in Uganda.⁴³ This was a randomized clinical trial that evaluated single high-dose amphotericin B (10 mg/kg) with fluconazole (1200 mg/day) and flucytosine (100 mg/kg/day) for 2-week induction therapy of cryptococcal meningitis compared to standard amphotericin deoxycholate (1 mg/kg/day) with flucytosine (100 mg/kg/day). The trial enrolled participants who were HIV positive with a first episode of cryptococcal meningitis diagnosed by cryptococcal antigen or India ink staining. Participants were excluded if they were pregnant, had already taken amphotericin or fluconazole for >48 hours, had a previous serious reaction to the study medications or were taking a medication that would be contraindicated with the study medications. In Uganda, the trial enrolled 163 participants in the control arm and 164 in the intervention arm for a total enrollment of 327 Ugandan participants. The control cohort will be drawn from Ugandan participants. If IV liposomal amphotericin B is used in the investigational cohort then they will be drawn from the intervention arm. If IV deoxycholate amphotericin B is used in the investigational cohort then they will be drawn from the control arm. We will compare the EFA of all the control participants to the interventional participants using multivariate mixed linear regression, adjusting for confounding factors such as CD4+ count, GCS<15 or not, prior exposure to ART or not and other important clinical factors. We will also compare 10-week survival in the

interventional and control cohorts, using multivariate Cox regression, adjusting for the same clinical factors as the mixed regression model.

This 2018 and 2022 WHO recommended regimen is based on a phase III randomized clinical trial demonstrating that:

- i) 1 week of IV AMB had equivalent survival as 2 weeks of IV AMB;²
- ii) 1 week of IV AMB combination therapy was less toxic than 2 weeks of IV AMB;² and
- iii) Adjunctive flucytosine had superior survival to adjunctive fluconazole.²

A DSMB review by the full committee will occur after 10 participants have been enrolled with >2 weeks of accrued data. A local Ugandan community member will be invited to attend open DSMB meetings. The DSMB safety reports will be submitted to the IRBs and regulatory authorities.

Timing of ART Initiation or Switch.

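### Section 11.4.1 reads an EFA above 0.30 as similar survival, but the protocol's own data show two amphotericin regimens above 0.30 whose survival differed with and without 5-FC

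*Combined protocol and SAP*

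**What the plan says.** Section 11.4.1 plans for 36 participants with a calculable EFA and an SD of about 0.20. It then explains how the result will be read. An EFA above 0.30 is to establish superiority over fluconazole 1200 mg and non-inferiority to the all-oral 5-FC + fluconazole regimen. An EFA of 0.35 is to establish non-inferiority to controls with a margin of 0.17. The paragraph closes by saying that above 0.30 "survival is relatively similar across antifungal regimens, as per section 2.5 and Figure 2.5". Earlier in the same section, once EFA passes about 0.30, "there is less obvious incremental gains in survival beyond this threshold".

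Other parts of the protocol bear on this:

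- Section 2.1, on the ACTA trial: amphotericin with 5-FC "had a 38% reduced mortality at 10-week follow-up when compared to fluconazole used in combination with AMB".
- Section 4.1, on the same phase III evidence: "Adjunctive flucytosine had superior survival to adjunctive fluconazole".
- Section 2.5, cited as the support: its text places the threshold at 0.20, with comparable survival among amphotericin regimens above it. Figure 2.5 is titled "Early Fungicidal Activity versus 26-week Survival with IV AMB + Fluconazole".

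**The concern.** The trial asks what happens when the 5-FC contribution is reduced on top of amphotericin and fluconazole. Section 2.6.1 names the main risk: fungal clearance and the mortality benefit could both suffer. A statement that survival is much the same for any regimen above 0.30 bears directly on that risk, and it sits in the text that governs interpretation.

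If the statement is wrong for regimens with and without 5-FC, an EFA above 0.30 could be reported as reassurance on survival even though the reduced dose had lost what 5-FC adds. Two features of the plan raise the stakes. Section 11.7 says the secondary endpoints are mainly descriptive and unpowered unless effects are large. Section 11.2 runs the primary EFA analysis when the last participant reaches 2 weeks, before 18-week survival is complete.

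**Working it through.** **1. The plan's own clearance statements.** Normal approximation, SE = √(0.20²/36 + SDc²/nc), two-sided 95% limits, inputs from Table 2.5.

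- EFA 0.30 against fluconazole 1200 mg (0.18, SD 0.11, n=30): SE = 0.0389, z = 0.12/0.0389 = 3.08, lower limit of the difference 0.044. Superiority reproduces.
- EFA 0.35 against the AMBITION single-dose arm (0.40, SD 0.13, n=407): the deficit is 0.05, with upper limit 0.05 + 1.96 × 0.0340 = 0.117, below 0.17. Non-inferiority reproduces.

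The clearance statements checked here are sound. The survival sentence is the one in question.

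**2. The survival sentence against the protocol's evidence.**

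| Regimen (Table 2.5) | EFA | SD | N | Above 0.30? |
|---|---|---|---|---|
| Amphotericin + 5-FC | 0.46 | 0.25 | 186 | yes |
| Amphotericin + fluconazole 1200 mg | 0.36 | 0.23 | 175 | yes |

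The reference column of the table is broken in the text available, so assigning these rows to ACTA is an inference. The Ns support it: 186 + 175 = 361, matching the 1-week and 2-week rows, 179 + 182 = 361. Both regimens clear 0.30, yet Sections 2.1 and 4.1 say survival differed in favour of 5-FC.

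**3. The cited support.** Section 2.5 gives 0.20, not 0.30. If its reference to amphotericin regimens means those with fluconazole, as the figure title suggests, it makes no comparison with and without 5-FC. If it is meant to include 5-FC regimens, the evidence in step 2 contradicts it as well.

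**4. How often would a cohort without any 5-FC effect clear 0.30?** Section 4.1 gives all participants amphotericin and fluconazole 1200 mg, so the amphotericin + fluconazole 1200 mg row (N=175) is a reasonable stand-in for the regimen with the 5-FC contribution removed.

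P(observed mean > 0.30) = Φ[(μ − 0.30)/(SD/√36)], with μ = 0.36:

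- SD 0.23 (that row): SE = 0.0383, z = 1.565, P = 94.1%.
- SD 0.20 (planning value): SE = 0.0333, z = 1.80, P = 96.4%.
- SD 0.44 (implied by Table 11.4.1): SE = 0.0733, z = 0.818, P = 79.3%. The implied SD is interval width/3.92 × √N. For N=30, (0.608 − 0.292)/3.92 × √30 = 0.44. Over all replicate sizes it is about 0.43 to 0.46, giving 78% to 80%.

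With the full 5-FC effect (μ = 0.46, SD 0.25), z = 0.16/0.0417 = 3.84 and P > 99.9%. The benchmark is passed in 94% of trials without a 5-FC effect and nearly always with one, so passing it says little about which holds.

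**5. Other no-5-FC amphotericin rows of Table 2.5**, each with its own SD, n=36:

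| Row | EFA (SD) | P(mean > 0.30) |
|---|---|---|
| 5 days + fluconazole 1200 mg | 0.30 (0.11) | 50% |
| Amphotericin alone, N=99 | 0.31 (0.15) | 66% |
| + fluconazole 800 mg, N=99 | 0.32 (0.10) | 88% |
| + fluconazole 800 mg, N=223 | 0.36 (0.25) | 92.5% |
| + fluconazole 1200 mg, N=23 | 0.41 (0.35) | 97% |
| + fluconazole 800 mg + sertraline | 0.43 (0.39) | 98% |
| 7 days + fluconazole 1200 mg | 0.38 (0.20) | 99% |
| + fluconazole 800 mg, N=22 | 0.38 (0.18) | 99.6% |
| + voriconazole (z = 0.14/0.0333 = 4.2) | 0.44 (0.20) | >99.9% |
| 1 mg/kg alone, N=49 | 0.48 (0.28) | >99.9% |

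Section 2.4 reports 0.52 for single-dose liposomal amphotericin + fluconazole without 5-FC. No SD is given. At an assumed 0.20, z = 0.22/0.0333 = 6.6 and P is about 100%.

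**The case against.** The strongest reply is that 0.30 is nowhere a success criterion. The objective (Section 3.1.1) and hypothesis (Section 11.3) concern fungal clearance, tested by adjusted regression against AMBITION controls (Section 4.1). Survival has its own objective, a 10-week Cox comparison and an 18-week endpoint. This stands. A reader might infer that the trial declares survival preserved whenever EFA passes 0.30, but the documents do not say so.

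It does not follow that the formal test would stop a wrong survival reading. As a cross-trial illustration, take a no-5-FC cohort (0.36, SD 0.23, n=36) against 0.40 (SD 0.13, n=164, the Ugandan intervention-arm size). SE = 0.0397, and Φ[(0.17 − 0.04)/0.0397 − 1.96] = 91% would meet the 0.17 margin. Against 0.46 (SD 0.25, n=186) the figure is 38%.

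Second, Section 2.5 concedes that EFA is an imperfect surrogate. That caveat concerns individual patients. The same section goes on to defend group EFA as associated with mortality, and Section 11.4.1 repeats no caveat.

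Third, Figure 2.5 is not shown, and the source behind the sentence on diminishing gains cannot be checked. The judgement on the figure rests on its title and the surrounding text.

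Three stronger readings should be resisted:

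- The 38% is not a percentage-point difference. Section 2.1 speaks of mortality reduced by 38%.
- Not every amphotericin regimen would clear 0.30. The probability is 50% for one row and 66% for another. For the 0.36 row it would be 35% if the lower 95% limit had to exceed 0.30 (Φ[1.565 − 1.96]), which the text does not require.
- The synopsis links EFA above 0.30 to 30–40% mortality, while Section 2.3 cites "1 week of IV AMB + flucytosine with 24% (27/113) 10-week mortality". This is not a clean contradiction. The first is a cross-trial association and the second is one arm, with a 95% Wilson interval of about 17% to 32.5%.

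**Conclusion.** The point holds as a fault in how the result is to be interpreted. The formal test and the clearance comparisons are not affected. The protocol's own randomised evidence has two amphotericin regimens above 0.30 with different survival, and they differ in exactly the component this trial reduces. The section and figure cited in support give a different threshold and, by title, a setting without 5-FC.

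The size is 94% (EFA 0.36, SD 0.23, n=36, observed mean above 0.30). It ranges from about 79% to 96% over the SDs considered for that row, and from 50% to nearly 100% across the no-5-FC amphotericin rows. This assumes approximate normality of the mean, that those rows can stand in for a regimen whose 5-FC contribution is lost, that the two key rows come from ACTA, and that the 38% is relative. The sentence should be corrected before the EFA result is read.

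**What to change.** In Section 11.4.1, delete the sentence that equates an EFA above 0.30 with similar survival across regimens. Keep the sentence on diminishing survival gains as cited background only. Add:

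> An EFA above 0.30 will not be taken as evidence that survival is preserved at the reduced 5-FC dose. EFA supports conclusions about fungal clearance only: non-inferiority to the AMBITION controls, and the stated comparisons with fluconazole monotherapy and with oral 5-FC + fluconazole. Statements on survival will rest on the planned adjusted 10-week Cox comparison with the AMBITION controls (Section 4.1) and the 18-week survival endpoint, reported with 95% confidence intervals and noted as not powered (Section 11.7).

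The added text should not limit EFA to the AMBITION comparison alone, because Sections 11.3 and 11.4.1 also plan clearance comparisons with fluconazole monotherapy and the oral regimen.

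The cost is wording only, with no new data or analysis. The sponsor loses a favourable interpretive sentence, and the survival evidence that remains will be imprecise.
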